#### **4.9. Data Management and Analysis**

Data will be collected by using pre-constructed pro forma. Following data collection and prior to data entry, all data will be carefully screened for accuracy.

Data entry will be done by using Microsoft Excel 2019. The data will be statistically analyzed by using computerized statistical software SPSS (Statistical Package for Social Science Version 21).

Data summarization for description will be done by showing frequency distribution tables and appropriate graphs. The parameters for clinical effectiveness and laboratory-defined adverse event gradings will be described by number, percentage in treatment group.

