Even where flucytosine (5FC) is available, it is often not administered because of overstated fears regarding toxicity (Loyse et al., 2013). The most serious drug-related adverse effect of 5FC is bone marrow suppression and hepatotoxicity (Vermes et al., 2000). In California's study, 5FC had been discontinued in over half of the patients because of cytopenia (Chuck & Sande, 1989). One patient in South Africa study also was discontinued 5FC because of thrombocytopenia on day-4 and the regimen was switched early to fluconazole (Bicanic et al., 2008). And also grade-4 neutropenia was recorded in 3.2% of the patients with 5FC (Molloy et al., 2018). But

in Thailand study, the treatment was well tolerated and there was no severe bone-marrow depression with 5FC (Brouwer et al., 2004).

Regarding amphotericin B Deoxycholate, its major drug-related adverse effects include nephrotoxicity and anemia (Bicanic et al., 2015). In Vietnam trial, Grade 3 and 4 anaemia were most prominent between amphotericin B plus flucytosine (35%) and amphotericin B plus fluconazole group (29%) (Day et al., 2013). Renal impairment occurs in nearly all patients treated with clinically significant doses of amphotericin. Fluconazole is relatively nontoxic, but reported to cause abnormalities in liver enzymes and very rarely, clinical hepatitis (Lampiris & Maddox, 2018).

Although WHO treatment guidelines recommend treatment regimen containing flucytosine as the preferred therapy, in clinical practice, treatment is highly variable due to drug costs, availability, and ability to monitor and manage drug-related toxicities (Perfect, 2010). A previous study was carried out in Mandalay for cryptococcal meningitis with fluconazole monotherapy by Than-Maung in 2006 and amphotericin B monotherapy by Myo-Thet-Naing in 2013 but the effectiveness and safety of amphotericin with flucytosine and fluconazole combination regime have not been studied in Myanmar. Thus, this study will provide information regarding the clinical effectiveness and safety of this treatment regimen for management of HIV-associated cryptococcal meningitis in Myanmar.

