## **1.2. Justification**

Cryptococcal meningitis is an AIDS-defining illness mostly caused by the fungus, *Cryptococcus neoformans*. In high-income countries, the use of amphotericin B in combination with a more expensive drug, flucytosine, is most effective for the management of cryptococcal meningitis; but access to flucytosine is severely limited in middle and low-income countries. In Myanmar, currently recommended regimen for cryptococcal meningitis are combination of amphotericin B with fluconazole. Although amphotericin plus flucytosine followed by fluconazole therapy is the currently preferred regimen in WHO treatment guidelines, it is not still commonly used in Myanmar clinical practice because of its limited availability. Therefore, the data regarding tolerability and clinical effectiveness of flucytosine are unavailable for Myanmar patients.

Although trials were carried out for investigating the effectiveness of flucytosine in the HIV population of Africa, the variability in drug response can occur

in Myanmar patients due to the racial and genetic differences and whether it is effective and safe for Myanmar people is a great curiosity question for clinicians and healthcare workers. In Myanmar, amphotericin plus flucytosine followed by fluconazole regimen will be supplied by National AIDS Program (NAP) and indicated in 2020. Thus, the documents for effectiveness and safety profile need to be established. This is the reason that the effectiveness and safety of amphotericin B with flucytosine and fluconazole combination therapy should be studied. From this study, it can provide information to physicians regarding the effectiveness as well as safety of those drugs in the management of cryptococcal meningitis in HIV patients.

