### **2.1.12. Safety**

In ACTA trial, they randomly assigned HIV-infected adults with cryptococcal meningitis to receive an oral regimen (fluconazole [1200 mg per day] plus

flucytosine [100 mg per kilogram of body weight per day] for 2 weeks), 1 week of amphotericin B (1 mg per kilogram per day), or 2 weeks of amphotericin B (1 mg per kilogram per day). Each patient assigned to receive amphotericin B was also randomly assigned to receive fluconazole or flucytosine as a partner drug. Laboratory-defined side effects were less frequent in the oral-regimen group than in the 1-week or 2-week amphotericin B groups. Grade 4 anemia developed in 0.9% of patients in the oral-regimen group, 4.9% of patients in 1-week amphotericin B groups, and 8.8% of patients in the 2-week amphotericin B group. And also Grade 3 anemia developed in 4% of patients in the oral-regimen group, 8.9% of patients in 1-week amphotericin B groups, and 17.5% of patients in the 2-week amphotericin B group. A grade 3 or 4 increase in the serum creatinine level developed in 4.9% of patients in the oral-regimen group, 6.2% of patients in the 1-week amphotericin B groups, and 8.8% of patients in the 2-week amphotericin B groups. Grade 4 hypokalemia developed in only one patient, most likely because preemptive electrolyte replacement was provided for patients receiving amphotericin B.

Grade 4 neutropenia was recorded in 3.2% of the patients who were taking a regimen that included 2 weeks of flucytosine, in 0.9% of those taking 1 week of flucytosine, and in 1.3% of those taking a flucytosine free regimen. A grade 4 increase in the alanine aminotransferase level developed in only two patients, one of whom was taking fluconazole. Clinical adverse events were frequent with all regimens, which was reflective of the severe immunosuppression in this patient population.

As a partner drug with amphotericin, 1week amphotericin and flucytosine group develop Grade 3 and 4 anaemia of 8.8% and 24.56 % in 2 weeks amphotericin and fluconazole group. (Molloy et al., 2018).

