In Vietnam trial, Grade 3 and 4 anaemia were most prominent between amphotericin B plus flucytosine (35%) and amphotericin B plus fluconazole group (29%). Grade 3 and 4 Neutropenia (9%) were similar between the two groups. 4% of amphotericin B plus flucytosine group develop Grade 3 and 4 thrombocytopenia with 3% in the fluconazole group. Grades 3 and 4 increase in aminotransferase level was 6% in flucytosine group and 14 % in fluconazole group (Day et al., 2013).

But in one cohort study of amphotericin B with fluconazole, none of the patients developed any serious Grade 3, 4 anaemia and elevated ALT level. Only 2 patients developed grade III hypokalemia and thrombocytopenia. And 7 patients

develop grade 3,4 neutropenia and 4 patients develop grade III elevated creatinine level. (Muzoora et al., 2011).

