#### **4.7. Sample Size Determination and Sampling Procedure**

##### **4.7.1. Sample Size Determination**

The sample size was calculated by using the following formula

$$z_{(1-\frac{\alpha}{2})}^2 p (1-p)$$

$$n = \frac{z_{(1-\frac{\alpha}{2})}^2 p (1-p)}{d^2}$$

Sample size for clinical safety,

Where,

p = Proportion of absence of grade III/IV anaemia in patients with HIV-associated cryptococcal meningitis infection after being treated with Amphotericin B, Flucytosine plus Fluconazole  
= 0.83 (Molloy et al., 2018)

z = Standard normal deviate = 1.96 (95% CI)

d = Absolute precision = 0.14

n = minimal required sample size = 27

Sample size for clinical effectiveness,

Where,

p = Proportion of improvement of headache in patients with HIV-associated cryptococcal meningitis infection after being treated with Amphotericin, Flucytosine plus Fluconazole  
= 0.8

z = Standard normal deviate = 1.96 (95% CI)

d = Absolute precision = 0.15

n = minimal required sample size = 27

So, the required sample size is 27.

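### The safety part is sized on anaemia alone and reported without intervals, so the tables will not show that a zero count in 27 patients still allows a true rate of up to about 13%

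*Combined protocol and SAP*

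**What the plan says.** Section 1.2 gives the reason for the study: "the data regarding tolerability and clinical effectiveness of flucytosine are unavailable for Myanmar patients". Section 1.1 names marrow suppression and liver toxicity as the gravest adverse effects of flucytosine, and lists anaemia with kidney damage as the main effects of amphotericin B.

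The only safety quantity in section 4.7.1 is "Proportion of absence of grade III/IV anaemia in patients with HIV-associated cryptococcal meningitis infection", taken as 0.83, with "d = Absolute precision = 0.14" and a normal deviate of 1.96 for a 95% confidence interval. The effectiveness calculation uses headache improvement. Both give 27, described as a minimum. Section 4.7.2 takes all admissions in the study period.

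For reporting, section 4.9 states that "laboratory-defined adverse event gradings will be described by number, percentage in treatment group". Table 9 lists seven laboratory abnormalities by single grade, Table 10 combines grades 3 and 4 for the three blood counts, and Table 11 shows bone marrow suppression, which section 4.10 defines so that severe anaemia alone qualifies. Each table is laid out by visit (baseline, day 7, day 14).

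Section 2.1.12 supplies background rates. For grade 4 neutropenia in the African trial it gives "in 0.9% of those taking 1 week of flucytosine". From the Vietnam trial it reports that "4% of amphotericin B plus flucytosine group develop Grade 3 and 4 thrombocytopenia", with grade 3/4 neutropenia at 9% and grade 3/4 aminotransferase increase at 6%.

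**The concern.** The sample size rests on the precision of a 95% interval, but the analysis section never asks for an interval. For anaemia, the reader can at least go back to the planned precision of 0.14. For neutropenia, thrombocytopenia and liver enzymes there is no planned precision at all, and these are where the toxicity specific to flucytosine would appear.

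Without an interval, a cell reading 0 (0%) does not show how little 27 patients can rule out. A cell with one event has the same problem. The results are meant to inform physicians as the regimen is introduced, so the tables should carry their own uncertainty.

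**Working it through.** **1. The plan's own figure.** n = z²p(1−p)/d², with z = 1.96.
- Safety: 1.96² × 0.83 × 0.17 / 0.14² = 27.66.
- Effectiveness: 1.96² × 0.80 × 0.20 / 0.15² = 27.32.

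The stated 27 is the truncated value; rounding up gives 28. The difference does not matter here.

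**2. Chance of a zero count.** With 27 patients assessed and true rate r, P(0) = (1 − r)^27. Rates are from section 2.1.12.

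| Event | Rate | Expected events | P(0 of 27) |
|---|---|---|---|
| Grade 4 neutropenia, 1 week of flucytosine | 0.9% | 0.24 | 78% |
| Grade 3/4 thrombocytopenia | 4% | 1.08 | 33% |
| Grade 3/4 aminotransferase increase | 6% | 1.62 | 19% |
| Grade 3/4 neutropenia | 9% | 2.43 | 8% |

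Zero is more likely than not only if r is below 1 − 0.5^(1/27) = 2.5%. Of the four rates, only the first is.

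**3. What small counts allow.** Exact (Clopper-Pearson) two-sided 95% limits:
- 0/27: upper limit 1 − 0.025^(1/27) = 12.8%. The one-sided 95% limit is 1 − 0.05^(1/27) = 10.5%, and the Wilson limit is 12.5%.
- 1/27 (3.7%): 0.1% to 19.0%.
- 2/27 (7.4%): 0.9% to 24.3%.

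The upper limit for zero events is about 14 times the quoted 0.9% (12.8/0.9) and lies above the quoted 9%.

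**4. Fewer patients assessed.** Section 2.1.13 quotes 14% mortality at two weeks in an earlier study. If that applied here (an assumption), 27 × 0.86 ≈ 23 patients would be assessed at day 14, and 0/23 has an upper limit of 1 − 0.025^(1/23) = 14.8%.

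**5. The composite in Table 11.** Because anaemia counts, zero is unlikely. From anaemia alone, P(0 of 27) is 8% at the 8.8% quoted in section 2.1.12 for the one-week regimen, and 0.7% at the 17% implied by the sizing (1 − 0.83).

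**The case against.** A reader might infer that the flucytosine toxicities will mostly print as zero and that the study will then declare the drug tolerable. The documents do not support this.
- **Zeros.** At the quoted rates, zero is the likelier result only for grade 4 neutropenia. The grade 3/4 rows of Table 10 would more probably show at least one event (92% for neutropenia at 9%), and a zero in Table 11 is unlikely.
- **Counts are shown.** The plan prints numbers beside percentages, so the small numbers are visible. What is missing is the interval.
- **No tolerability conclusion is planned.** The fourth objective is to describe safety. Section 1.1 does cite a Thai study in which "the treatment was well tolerated and there was no severe bone-marrow depression with 5FC", without a denominator, but it sets this beside contrary reports and draws no conclusion that toxicity is absent. That a zero would be misread is a risk, not something in the plan.
- **Zero is not uninformative.** It is about ten times as probable at 0.9% as at 9% (78% against 8%). The accurate statement is that the 95% interval does not exclude 9%.

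These points narrow the concern but do not remove it. Nor does the descriptive design: an interval is itself descriptive, and the sample was sized for one. It is true that 27 is a minimum, but a few more patients change little: 0/28 still allows 12.3%, and zero events would exclude a 5% rate only with 72 patients (59 with a one-sided limit).

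One objection limits the remedy. Tables 9 to 11 count patients by visit. Events between visits, or in patients who die before a visit, are not captured, so a limit on a day-7 cell describes patients assessed on day 7. It would be wrong to claim that rates of a toxicity above 13% had been excluded.

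**Conclusion.** The point holds as a cheap improvement to the reporting. The safety part was sized on anaemia only and no interval is planned. A zero count, likely for grade 4 neutropenia and possible for the other severe events, remains compatible with a true rate up to 12.8% when 27 patients are assessed; a single event is compatible with 0.1% to 19.0%.

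This rests on three assumptions:
- Patients are independent and 27 are assessed at the visit in question. The limit changes with the number reached, for example to 14.8% with 23.
- The background rates carry over. The documents do not give the duration of flucytosine behind the Vietnam rates, and they quote no grade 3/4 neutropenia or thrombocytopenia rate for a one-week course. If those rates were below about 2.5%, zero would be the likelier result there too.
- The limits refer to findings at day 7 or day 14, not to cumulative incidence.

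**What to change.** 1. In section 4.9 and Tables 9 to 11, give the number of patients assessed at each visit and the exact (Clopper-Pearson) 95% interval beside every post-baseline grade 3, grade 4 and bone marrow suppression count, including zero cells. This is 36 intervals: 28 in Table 9 (7 abnormalities × 2 grades × 2 visits), 6 in Table 10 and 2 in Table 11. State that each has 95% coverage individually, not jointly.
2. In section 4.7.1, state that 27 was set on anaemia (safety) and headache (effectiveness) only, and that a zero count in 27 assessed patients leaves rates up to about 13% possible.
3. Report an unobserved toxicity as not observed at day 7 or day 14 among the n assessed, with its upper 95% limit, and not as absent.

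The cost is a few table columns, two or three sentences, and a less favourable safety statement. No additional patients or data items are needed.

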#### **4.10. Operational Definitions**

##### **(1) HIV-seropositive patient**

Patients who have been diagnosed as HIV infected patients by laboratory diagnostics tests in Myanmar. HIV testing strategies for HIV confirmation include three HIV antibody tests namely Determine (HIV-1/2) ICT, Uni-Gold (HIV) ICT and STAT-PAK (HIV 1/2) ICT (National AIDS Programme, 2017).

##### **(2) Cryptococcal meningitis in patients with HIV infection**

HIV-seropositive patient with symptoms and signs consistent with the diagnosis of cryptococcal meningitis and one or more of positive India ink test, positive cryptococcal antigen test in CSF.

##### **(3) Clinical Effectiveness**

Clinical effectiveness will be assessed by using these parameters such as headache, fever, convulsion, abnormal mental status and death.

###### **(i) Severity of headache**

Severity of headache is assessed by using Numerical rating scale (NRS). The NRS score range from zero to 10. Headache severity will be categorized according to the number given by patients for their headache. Headache will be categorized as no pain, mild, moderate, severe, and intolerable when scores are 0, 1-3, 4-6, 7-9, and 10. Headache will be evaluated by administration of a headache questionnaire at day-1, day-7 and day-14.

###### **(ii) Fever**

It is defined as rise in body temperature above 37 °C (98.6 °F) in the morning.

(iii) Convulsion

It is defined as a medical condition where body muscles contract and relax rapidly and repeatedly, resulting in uncontrolled actions of the body.

(iv) Abnormal mental status

It is defined as patients is somnolent, lethargy, disoriented and disruptions in perception and behavior.

(4) Clinical safety

Clinical safety will be assessed by laboratory defined adverse events. Adverse event is defined as any untoward medical occurrence in a subject to whom a medicinal product has been administered including occurrences which are not necessarily caused by or related to that product (Division of AIDS, 2017). Laboratory parameters (hematological and biochemical parameters) such as HGB, NEUT, PLT, ALT, AST, serum creatinine, serum potassium level will be graded according to DAIDS grading in appendix 3. Bone marrow suppression is defined as Grade 3 and 4 adverse events in one or more of anaemia, neutropenia and thrombocytopenia.

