#### **3.2. Objectives**

1. To find out the back-ground characteristics of patients with HIV-associated cryptococcal meningitis
2. To describe the clinical effectiveness of amphotericin B with flucytosine-fluconazole combination therapy by assessing clinical parameters at day 1, day 7 and day 14
3. To determine the severity of headache before and after treatment by numerical rating scale
4. To describe the clinical safety of amphotericin B with flucytosine-fluconazole combination therapy by assessing hematological and biochemical parameters by DAIDS grading at baseline, day 7 and day 14

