#### **4.11. Ethical Considerations**

The study will be hospital-based descriptive study regarding the clinical effectiveness and safety of amphotericin B with flucytosine-fluconazole combination therapy for treatment of HIV-associated cryptococcal meningitis. In this study, all patients according to selection criteria admitted to inpatient departments of SHW, SHM and SHT will be included. The participants eligible to the selection criteria will be invited to voluntary participation in the study and then explained in details about the study by the investigator with the information sheet of informed consent form (Part-I).

Only after they have understood the nature of study, objectives, methodology, procedure and duration, they can voluntarily take part in the study or they have right to refuse or withdraw at any time from the study without penalty of loss of benefit to which he or she would otherwise be entitled. If they agree, the written informed consent will be obtained by using informed consent form (Part-II) from all participants or from parents/relatives/next of kin if the patient could not provide the consent.

[figure not shown]
The study will be done under the supervision of a physician. The study will collect data under routine management. No new drugs will be administered and no treatment will be restricted for the purpose of thesis. The participants will be closely monitored throughout the research process. If any adverse reactions occur, the researcher will immediately inform to the physician and urgent treatment will be given and the necessary actions will be taken according to the standard treatment procedure.

The investigator will strictly maintain the rules of privacy and confidentiality. The name of patients will not be mentioned in this study. Only coded system will be used and research information will be kept by a password-protected file in the investigator's personal computer. All the personal information of the subject in Pro forma will be destroyed and the personal information in the investigator's personal computer will be deleted after the study period. The presentation on research data will be used in medical workshop, seminars and conference and the data will also be published for the academic purposes- only in thesis, papers and medical journals if necessary.

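### Clinical adverse events outside five effectiveness parameters are neither recorded nor tabulated, so the data support a statement on laboratory safety only

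*Combined protocol and SAP*

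**What the plan says.** Section 4.10, item (4), sets the method: "Clinical safety will be assessed by laboratory defined adverse events". It then gives the general definition: "Adverse event is defined as any untoward medical occurrence in a subject to whom a medicinal product has been administered", and adds that the event need not be related to the product. The next sentence names what will be graded: parameters "such as HGB, NEUT, PLT, ALT, AST, serum creatinine, serum potassium level will be graded according to DAIDS grading". Objective 4 in Section 3.2 has the same scope: safety is to be described "by assessing hematological and biochemical parameters by DAIDS grading at baseline, day 7 and day 14".

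Section 4.11 deals with reactions as a matter of care: "If any adverse reactions occur, the researcher will immediately inform to the physician and urgent treatment will be given". It gives no step for recording or counting them.

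The background makes clinical events foreseeable. Section 2.1.12 says of the large African trial: "Clinical adverse events were frequent with all regimens, which was reflective of the severe immunosuppression in this patient population". Section 1.2 justifies the study partly because "the data regarding tolerability and clinical effectiveness of flucytosine are unavailable for Myanmar patients".

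The title (repeated on the pro forma), the aim (3.1) and the research question (3.3) all speak of safety without qualification.

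**The concern.** The definition of an adverse event and the data to be collected do not match. Under the definition, any clinical event during treatment counts. Under the data plan, only seven laboratory values count as safety. A reaction could be noticed, notified and treated under Section 4.11 and still leave no trace in the study data.

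What is at stake is the conclusion. The study is meant to inform physicians about safety as the national programme brings the regimen into use, and it cites missing tolerability data as a reason to do it. Seven laboratory values read at baseline and two later days do not answer a tolerability question. Nor can the gap be reliably filled afterwards, because nothing requires these events to be entered in the study data.

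**Working it through.** This is mainly a question of what is collected, so the check sets the places side by side.

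**1. Where a clinical adverse event could be recorded or reported**
- *Methods (4.8):* the safety items are haemoglobin, neutrophils, platelets, ALT, AST, creatinine and potassium, taken from charts at baseline, day 7 and day 14.
- *Pro forma (Annex 1), sections I to X:* section X has rows for those seven values only. The list in Section 4.10 is introduced loosely, but the pro forma and Table 9 fix it at seven. Section V pre-prints the planned regimen and has no field for a stop or change of drug, although Section 1.1 cites earlier studies in which flucytosine was stopped (there for blood-count reasons). No section is for clinical adverse events.
- *Analysis (4.9):* counts and percentages of effectiveness parameters and laboratory gradings only.
- *Tables 9 to 11:* laboratory grades, grade 3 and 4 haematological events, and bone marrow suppression.
- *Annex 3:* the DAIDS extract lists laboratory parameters only.

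**2. Clinical items that are collected**
Headache, fever, convulsion and abnormal mental status have pro forma fields at days 1, 7 and 14 and rows in Table 8. Death has a row in Table 8 but no field in pro forma sections I to X. All five are classed as effectiveness. The four symptom fields record status on set days, with fever as a morning reading, so an event that starts and resolves between those days has no place.

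**3. The planned sample size**
The formula in Section 4.7.1 is n = z² p(1 − p)/d², with z = 1.96.
- Safety, p = 0.83, d = 0.14: 3.8416 × 0.1411 / 0.0196 = 27.66.
- Effectiveness, p = 0.8, d = 0.15: 3.8416 × 0.16 / 0.0225 = 27.32.

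Both round up to 28, against 27 stated. The one-patient difference does not matter here, and n = 27 is used below.

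**4. Illustration of scale**
The documents give no rate for clinical reactions, so the rates r are assumptions. P(at least one event in 27) = 1 − (1 − r)^27:
- r = 1%: 24%
- r = 5%: 75%
- r = 10%: 94%
- r = 20%: 99.8%

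If events were recorded and none occurred in 27 patients, the one-sided 95% upper bound on the rate would be 1 − 0.05^(1/27) = 10.5%. Without a recording field, neither a count nor this bound can be given.

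**The case against.** The case for the plan as written has real substance.

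- *The restriction is open.* Objective 4, Section 4.10 and the title of Table 9 all say that safety means laboratory parameters. This stands, but the study title, aim and research question do not carry the limit.
- *The choice follows the protocol's rationale.* The toxicities it stresses in Sections 1.1 and 2.1.11 are bone marrow suppression, liver and kidney toxicity, anaemia and hypokalaemia, and the seven values cover them. This stands as a reason to measure those values. It does not make them a measure of tolerability.
- *Clinical events are partly captured.* Under the protocol's broad definition, a convulsion newly present at day 7 is an adverse event, and it is counted. This stands and limits the point to events outside the five parameters.
- *The supporting passages are weaker than they look.* Section 4.11 is conditional. Section 2.1.12 links the clinical events to immunosuppression, so it does not show that drug reactions are expected. In a single-group descriptive study such counts could not be attributed to the regimen. All of this stands and governs how a new table should be worded.

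A reader might go further and infer that the study will report zero clinical reactions, or that it captures no clinical events at all. The documents support neither. No table has a row in which a zero would appear, and an event not collected is different from a reported zero. Five clinical parameters are tabulated in Table 8.

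**Conclusion.** The point holds within those limits. Clinical adverse events other than headache, fever, convulsion, abnormal mental status and death are neither recorded on the pro forma nor tabulated, although the protocol's own definition includes them and Section 4.11 provides for their notification. The laboratory results remain valid. What lacks support is the unqualified word safety in the title, aim and research question, and any answer to the tolerability gap cited in Section 1.2.

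No numerical size can be put on the loss. The figures of 75%, 94% and 99.8% rest on assumed event rates and show only that such events could well occur among 27 patients. The conclusion itself rests on reading the definitions, methods, analysis section, dummy tables and pro forma. The consent annex was not examined. This should be changed before data collection, since it is cheap and alters what the study can conclude.

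**What to change.** Make three additions:

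1. A pro forma section for clinical adverse events up to day 14: event, onset day, severity grade, serious yes/no, and action taken, including whether a study drug was stopped or changed. Fill it from the notification in Section 4.11 and from the charts already reviewed at days 7 and 14.
2. Clinical grading criteria in Annex 3, because the present extract cannot grade a clinical event.
3. One table with the number and percentage of patients with any clinical event, and with any grade 3 or 4 clinical event. A note should say that a single-group study cannot attribute these events to the regimen.

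The cost is a few minutes per patient. There is no new procedure and no change in sample size or treatment. Chart-based and passive capture may under-report, and the report should say so.

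If this is not done, change safety to laboratory safety in the title, aim, research question and conclusion.
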